### 9.4.2.2 Microbiological Assessment

The By-Pathogen Microbiological Response will be assessed in the micro-ITT and ME Analysis Sets for each causative organism using the categories for outcome as follows.

- **Success** includes:
  - Eradication: the baseline causative pathogen was absent from repeat culture(s).
  - Presumed eradication: the IACR was Success, and culture was not repeated.
- **Failure** includes:
  - Persistence: the baseline causative pathogen was isolated in repeat culture(s).
  - Presumed persistence: the IACR was Failure and a culture was not repeated.
- **Indeterminate:**
  - The IACR was Indeterminate, and culture was not repeated.

The By-Subject Microbiological Response will be programmatically determined at TOC for each subject using the By-Pathogen Microbiological Response for each Baseline causative pathogen. For a subject to have a By-subject Microbiological Response of Success, the response for each Baseline pathogen must be Success (i.e., Eradication or Presumed Eradication). If the response for any Baseline pathogen is Failure (i.e., Persistence or Presumed Persistence), the subject will be considered to have a By-Subject Microbiological Response of Failure. A By-Subject Microbiological Response of Indeterminate will be assigned if all Baseline pathogens have a Microbiological Response of Indeterminate.

New bacteria isolated from respiratory or blood culture will be assessed separately from the outcomes listed above as follows:

- **Superinfection:**

- New pathogen(s) (i.e., pathogen(s) not present at baseline) identified in post-baseline culture(s) through the TOC Visit with persistent signs and symptoms of CABP (i.e., IACR of Failure at the TOC Visit, such that additional antibacterial therapy is necessary for the current episode of CABP).

- **Colonization:**

- New pathogen(s), (i.e., pathogen(s) not present at baseline) identified in at least 2 post-baseline cultures through the TOC Visit but signs and symptoms of CABP have resolved, (i.e., IACR of Success at the TOC Visit, such that no additional antibacterial therapy is necessary for the current episode of CABP).

- **Development of Decreasing Susceptibility:**

- Increase in MIC ( $\geq 4x$ ) or  $\geq 6$  mm decrease from baseline in disk inhibition zone diameter to the study drug received for a pathogen isolated at baseline and subsequently isolated from a blood or lower respiratory tract specimen.

#### 9.4.3 Safety Analysis Variables

Safety will be assessed by monitoring vital signs, ECG measurements, clinical laboratory parameters, and AEs.

#### 9.4.4 Pharmacokinetic Analysis Variables

Population PK modeling will be performed to determine the model-predicted plasma concentration time curves of lefamulin for each subject. Calculated PK will enable descriptive statistical analysis of PK variables such as the maximum observed drug concentration ( $C_{max}$ ) and area under the concentration-time curve (AUC) for lefamulin. Individual 24h AUC values from Day 1 obtained from the population PK model will be used for the PK/PD analysis focusing on efficacy. The PK based on population PK as well as a PK/PD analysis will be reported separately.

#### 9.4.5 Other Variables

Exploratory evaluation of a variety of health utilization variables (e.g., length of hospital stay, duration of antibiotic therapy, discharge status, discharge destination) as well as a PRO instrument (SF-12) will be performed. Details for this exploratory analysis will be presented in a separate SAP and results will be presented in a stand-alone clinical study report.

### 9.5 Demographic and Baseline Characteristics

Enrollment, protocol deviations, and discontinuations from the study drug and the study will be summarized by treatment group. Demographics (age, race, ethnicity and sex), medical and surgical history, baseline assessment of the clinical signs and symptoms, microbiological assessment, and study drug administration will also be summarized by treatment group. Differences between treatment groups will be analyzed using the chi-square or Fisher's exact test for dichotomous variables and the Wilcoxon Rank Sum test for ordinal and continuous variables.

### 9.6 Efficacy Analysis

For all efficacy analyses, subject data will be analyzed in the group to which the subject was randomized. For the stratified analysis of the primary efficacy outcome and for the primary analysis for the EMA, subjects who are randomized to the wrong stratum will be analyzed in the stratum to which they were randomized.

#### 9.6.1 Primary Efficacy Analysis

The primary efficacy outcome (FDA) is the proportion of responders for ECR at  $96 \pm 24$  hours following the first dose of study drug in the ITT Analysis Set. Each subject will be programmatically categorized as a Responder, Non-responder or Indeterminate based on data on the eCRF. Subjects who are missing data required to determine an ECR or who are lost to follow up are defined as Indeterminate for the primary analysis and are included in the denominator for the calculation of the responder rate. Thus, subjects with an ECR of Indeterminate are considered non-responders for the primary analysis. The number and percentage of subjects in each treatment group in each response category will be reported.

The null and alternative hypotheses are:

$$H_0: P_1 - P_2 \leq -\Delta$$

$$H_1: P_1 - P_2 > -\Delta$$

Where  $P_1$  = the primary efficacy outcome rate in the lefamulin group

$P_2$  = the primary efficacy outcome rate in the moxifloxacin group

$\Delta$  = the non-inferiority margin

The NI hypothesis test is a 1-sided hypothesis test performed at the 2.5% level of significance. This is based on the lower limit of the 2-sided 95% confidence interval (CI) for the observed difference in the ECR (lefamulin group minus the moxifloxacin group). The CI

will be calculated using an unadjusted continuity corrected Z-statistic. If the lower limit of the 95% CI for the difference in responder rates in the ITT Analysis Set is greater than -12.5%, the null hypothesis will be rejected and the NI of lefamulin to moxifloxacin will be concluded.

Additional analyses of the primary efficacy analysis will be conducted. ECR will be assessed separately across the geographic regions, prior antibiotic use, and PORT risk class strata. For each geographic region, prior antibiotic use, and PORT risk class stratum, a 2-sided 95% CI for the observed difference in ECR responder rates will be calculated for the ITT Analysis Set. Sensitivity analyses of ECR include determination of an adjusted 95% CI (adjusted for the randomization stratification factors) and considering all subjects with missing data (i.e., Indeterminates) at  $96 \pm 24$  hours after the first dose of study drug as responders for ECR (these subjects are considered non-responders in the primary analysis). For the second sensitivity analysis, an unstratified 95% CI will be computed for the difference in the responder rates between lefamulin and moxifloxacin. Subgroup analyses of the primary efficacy outcome will also be conducted for descriptive purposes and will be detailed in the SAP.

For the EMA primary analysis (secondary analysis for the FDA), the number and percentage of subjects in each treatment group with an IACR of Success, Failure and Indeterminate (by definition Indeterminates are not included in the CE-TOC Analysis Set) at TOC will be reported in the mITT and CE-TOC Analysis Sets. Subjects who have an IACR of Failure at EOT will be considered to have an IACR of Failure at TOC. The primary analysis for the EMA will utilize 2-sided adjusted (for the randomization stratification factors) 95% CIs calculated using the method of Miettinen-Nurminen. If the lower limit of the 95% CI for the difference in success rates in both the mITT and CE-TOC Analysis Sets is greater than -10%, the NI of lefamulin to moxifloxacin will be concluded. Two-sided unstratified 95% CIs will be calculated for the difference in success rates at TOC in the mITT and CE-TOC Analysis Sets (FDA secondary outcome).

Additional analyses of the EMA primary efficacy outcome will be conducted. IACR at TOC will be assessed separately across the geographic regions, prior antibiotic use, and PORT risk class strata in the mITT and CE-TOC Analysis Sets. For each geographic region, prior antibiotic use, and PORT risk class stratum, a 2-sided 95% CI for the observed difference success rates will be calculated for the ITT and CE-TOC Analysis Sets. Sensitivity analyses of IACR include determination of unstratified 95% CI and considering all subjects with missing data (i.e., Indeterminates) as successes for IACR (these subjects are considered failures in the EMA primary analysis). For the second sensitivity analysis, a stratified 95% CI will be computed for the difference in the success rates between lefamulin and moxifloxacin. Subgroup analyses of the EMA primary efficacy outcome will also be conducted for descriptive purposes and will be detailed in the EMA SAP.

### 9.6.2 Secondary Efficacy Analyses

The number and percentage of subjects categorized as Responder, Non-responder and Indeterminate for the primary efficacy outcome of ECR will also be presented for the microITT Analysis Set and a 2-sided unstratified 95% CI for the difference in responder rate

will be calculated using a continuity-corrected Z-statistic. However, the formal test of NI will be conducted in the weighted (based on the inverse variance of each effect size) pooled population from this study and a second study in CABP.

The number and percentage of subjects categorized as Responder, Non-responder and Indeterminate for ECR plus improvement in vital signs will also be presented for the ITT Analysis Set and a 2-sided unstratified 95% CI for the difference in responder rate will be calculated using a continuity-corrected Z-statistic.

The number and percentage of subjects in each treatment group with an IACR of Success, Failure and Indeterminate (by definition Indeterminates are not included in the ME-TOC Analysis Set) at TOC will be reported in the microITT and ME-TOC Analysis Sets. Subjects who have an IACR of Failure at EOT will be considered to have an IACR of Failure at TOC. Two-sided unstratified 95% CIs will be calculated for the difference in success rates.

The By-Pathogen Microbiologic Response (by definition, subjects with an Indeterminate Microbiologic Response are excluded from the ME-TOC Analysis Set) will be provided for the microITT and ME-TOC Analysis sets at TOC.

All-cause mortality (ACM) through Day 28 will also be summarized in the ITT Analysis Set. Subjects who are lost to follow-up will be considered failures (i.e., deceased) for this analysis. A 2-sided unstratified 95% CI will be calculated for the treatment difference in ACM.

### 9.6.3 Additional Efficacy Analyses

Additional efficacy analyses will be conducted to support the efficacy findings for the primary and secondary outcomes. Confidence intervals for proportions will be determined for descriptive purposes, as indicated below, but no conclusions of NI will be made.

The number and percentage of subjects who are a Responder for ECR, the number and percentage of subjects who have an IACR of Success at TOC, and the number and percentage of subjects who are a sustained success at LFU will be presented by baseline pathogen in the microITT, ME-TOC (IACR only), and ME-LFU (sustained success only) Analysis Sets.

The number and percentage of subjects in each treatment group with an IACR of Success, Failure and Indeterminate (by definition subjects with an IACR of Indeterminate are not included in the CE Analysis Sets) at EOT in the mITT and CE-EOT Analysis Sets. Two-sided unstratified 95% CIs will be calculated for the difference in IACR success rates. The number and percentage of subjects with a Sustained Success, Relapse, Failure, and Indeterminate response as assessed by the Investigator at the LFU Visit will be summarized for the mITT and CE-LFU Analysis Sets. Failure is at LFU defined as a subject who had an IACR of failure at the TOC visit.

The By-Subject Microbiologic Response (by definition, subjects with an Indeterminate Microbiologic Response are excluded from the ME-TOC Analysis Set) will be provided for

the microITT and ME-TOC Analysis sets at TOC. Two-sided unstratified 95% CIs will be provided for the difference in the By-Subject Microbiologic Response success rate.

## 9.7 Safety Analysis

Safety will be evaluated in the Safety Analysis Set by presenting summaries of AEs, routine clinical laboratory evaluations, ECGs, and vital signs in the 2 treatment groups. Subjects who receive the wrong study drug for their entire course of treatment will be analyzed in the group based on the drug received.

Summary tables will be provided for all TEAEs. A TEAE is defined as an AE with a start date and time on or after the first dose of study drug. Adverse events will be coded using the Medical Dictionary for Regulatory Activities (MedDRA®). The number and percentage of subjects with TEAEs will be tabulated by system organ class (SOC) and MedDRA Preferred Term for each treatment group and by severity and relationship to treatment.

Adverse events leading to premature discontinuation from the study drug and serious TEAEs will be presented either in a table or a listing.

Change from baseline to each scheduled evaluation and the overall worst post-baseline in clinical laboratory variables will be summarized by treatment group. The number and percent of subjects with treatment-emergent potentially clinically significant (PCS) laboratory values will be tabulated for each treatment group. Treatment-emergent PCS laboratory tests are those in which the Baseline value is not PCS and the post-baseline value is PCS. PCS will be defined based on the pre-specified criteria outlined in the statistical analysis plan.

Change from baseline to each scheduled evaluation and the overall worst post-baseline for RR interval, PR interval, QRS interval, QT interval, and QT interval corrected with Fridericia from the ECG will be summarized for each treatment group with the mean, standard deviation, minimum value, and maximum value. The triplicate values will be averaged for each subject before analysis. An outlier analysis will also be provided based on the worst post-baseline value.

Descriptive statistics of vital signs and the change from baseline to each scheduled evaluation will be summarized by treatment group at each study visit and the worst overall post-baseline. The number and percent of subjects with treatment-emergent PCS values will be tabulated for each treatment group.

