**NOTE:** Hospitalization is not a requirement for this study. However, all subjects, including Outpatients, must be evaluated in person by study personnel at the following time points/visits: Screening/Baseline; Day 1; during each IV administration, 96 ± 24 hours after the first dose of study drug; End of Treatment (EOT); Test of Cure (TOC); and Late Follow-up (LFU).

- a: Perform Screening/Baseline assessments within 24 hours before first dose of IV study drug. Administration of study drug should begin as soon as possible after the diagnosis of CABP. Assessments performed as part of routine standard of care prior to consent (e.g., chest X-ray, blood culture) may be used to satisfy study screening requirements; however, no study specific procedures may be performed prior to informed consent.
- b: Day 1 is the first day of study drug administration; subsequent study days are consecutive calendar days.
- c: Days 4 to 7: Subjects receiving 7 days of randomized study drug.
- d: [Days 4 to 10: Subjects receiving 10 days of randomized study drug.]
- e: Perform EOT assessments at the study site within 2 days (1 day preferred) after the last dose of study drug or at the time of premature discontinuation of study drug or early withdrawal from study. EOT assessments resulting from premature discontinuation of study drug should be done in place of the regular study visit on Days 1 to 7 (or Days 1 to 10, as applicable).
- f: Perform TOC assessments at the study site 5–10 days after the last dose of study drug. All subjects will have a TOC Visit irrespective of early clinical failure or receipt of an alternative antibiotic.
- g: Perform LFU assessments at the study site on Day 30 ± 3 days. All subjects will have a LFU Visit irrespective of early clinical failure or receipt of an alternative antibiotic.
- h: Obtain informed consent before initiating any study assessments or procedures.
- i: Randomization may occur at either Screening or on Day 1 prior to receipt of the first dose of study drug.

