- j: Record vital signs (heart rate, blood pressure, respiratory rate, body temperature), O2 saturation, and supplemental oxygen usage daily on days the subject is seen in person (i.e., at baseline, daily while the subject is hospitalized [record vital signs associated with highest temperature], daily while the subject is on IV therapy, at in-person visits while the subject is taking oral study drug as an outpatient), and at EOT and TOC. Record vital signs, O2 saturation, and supplemental oxygen usage at LFU if medically indicated. If Screening and Day 1 occur on the same day, vital signs should be obtained as part of the Screening evaluation (prior to administration of any study drug) and repeated as part of the Day 1 assessment (record the vital signs associated with the highest temperature post dosing). If EOT and the last day of study drug are the same day, vital signs do not need to be repeated, they may be recorded once on that day (i.e., as part of the EOT assessment).
- k: Evaluate signs and symptoms of CABP at baseline, daily while receiving study drug and at EOT, TOC, and LFU. Signs and symptoms are not obtained at TOC or LFU if the subject was previously deemed to have an IACR of Failure. Subjects who are receiving medication at home may be contacted by phone to track signs and symptoms of CABP if an in-person assessment is not required or planned for that day. **EXCEPTION: Subjects must have a visit at the study site that is 96 ± 24 hours after the first dose of study drug to assess CABP signs and symptoms for calculation of ECR.** Study personnel will inform subjects as to the timing of this visit. If Screening and Day 1 are the same day, signs and symptoms of CABP do not need to be repeated on Day 1. If EOT and the last day of study drug are the same day, signs and symptoms of CABP should be done only once on that day (i.e., as part of the EOT assessment).
- l: Record AEs from the signing of the ICF through TOC and SAEs from signing of the ICF through LFU. Study personnel will follow unresolved AEs and SAEs present at LFU until resolution or stabilization.

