## 7 ADVERSE EVENTS

An adverse event (AE) is any untoward medical occurrence in a subject or clinical investigation subject administered a pharmaceutical product that does not necessarily have a causal relationship with this treatment. An AE can therefore be any unfavorable and unintended sign (including an abnormal laboratory finding), symptom, or disease temporally associated with the use of an investigational product, whether or not related to the investigational medicinal product.

Any pre-existing conditions or signs and/or symptoms present in a subject prior to the start of the study (i.e., before informed consent) should be recorded as medical/surgical history. Any medical occurrences which are new or worsened from the time of informed consent and up to and including the final visit must be reported as AEs or SAEs. All AEs and SAEs must be recorded irrespective of whether they are considered drug related. NOTE: lack of efficacy/clinical failure does not have to be recorded as an AE unless it is an SAE.

Subjects will be monitored throughout the study for adverse reactions to the study medications and/or procedures at each study visit. Questions will be posed in a non-leading manner so as not to bias the response. In addition to questioning at specific time points, subjects will be encouraged to spontaneously report any AEs. Any subject with an AE, SAE or clinically significant abnormal laboratory test value will be evaluated by the Investigator, or a monitoring physician, and will be treated and/or followed up until the symptoms or values have resolved or are assessed as stable by the by the Investigator. A physician, either at the Investigative site or at a nearby hospital emergency room, will administer treatment of any SAEs. Where appropriate, medical tests and examinations may be performed to ensure that an AE has fully resolved.

Adverse events will be monitored throughout the study from the time a subject is consented through the TOC visit; SAEs are to be collected from the time of consent through the LFU visit. Whenever possible, a specific disease or syndrome rather than individual associated signs and symptoms should be identified by the Investigator and recorded on the subject's eCRF. However, if an observed or reported sign or symptom is not considered a component of a specific disease or syndrome by the Investigator, it should be recorded as a separate AE on the subject's eCRF.

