Each AE or SAE reported will be assessed for intensity and the date and time of onset (if available), time relationship to dosing, duration, and outcome of each event will be noted.

Laboratory abnormalities are not considered AEs unless they are associated with clinical signs and symptoms or require medical intervention. Clinically significant abnormal clinical laboratory findings or other abnormal assessments that are associated with the disease being studied, unless judged by the Investigator as more severe than expected for the subject's condition, or that are present or detected at the start of the study and do not worsen, will not be reported as AEs or SAEs.

The Investigator will exercise medical and scientific judgment in deciding whether an abnormal clinical laboratory finding or other abnormal assessment is clinically significant.

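### Section 9.7 defines a TEAE by its start alone, so an AE that begins between consent and first dose and worsens on study drug is missed unless the worsening is logged as a new AE

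*Protocol*

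**What the plan says.** Protocol Section 9.7 (Safety Analysis) gives the definition: "A TEAE is defined as an AE with a start date and time on or after the first dose of study drug". TEAE counts by system organ class and Preferred Term, by severity and by relationship to treatment are built on it. The same section limits the serious-event output to serious TEAEs, but puts no such limit on AEs leading to premature discontinuation of study drug. The synopsis (Statistical Methods) lists SAEs, deaths and discontinuations beside TEAEs, with no treatment-emergent restriction.

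Collection starts before dosing. Table 3, footnote l, reads: "Record AEs from the signing of the ICF through TOC and SAEs from signing of the ICF through LFU". Footnote a sets the timing of screening: "Perform Screening/Baseline assessments within 24 hours before first dose of IV study drug".

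Section 7 (Adverse Events) sends conditions present before consent to medical history, and makes reportable whatever is "new or worsened from the time of informed consent" up to the final visit. For each reported event it lists intensity, onset date and time where available, time relationship to dosing, duration and outcome. It mentions no date of a change in severity, and it gives no instruction for the case where an AE already on record becomes worse.

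**The concern.** Section 7 counts worsening as something to report; the definition in 9.7 does not carry worsening over. An event that arises after consent but before dosing is already an AE with a pre-dose onset. If it becomes more severe, or serious, once the subject is on study drug, the start-only rule still classes it as not treatment-emergent.

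Worsening under treatment is part of the safety comparison. The enrolled subjects are acutely ill (PORT Risk Class III or above), so some events may begin around enrolment and intensify after dosing. At stake is the completeness of the TEAE tables and of the serious-TEAE output. No efficacy conclusion is touched.

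**Working it through.** No arithmetic applies: the point concerns a definition, and the protocol gives no rate of pre-dose AEs or of their worsening. The check applies the 9.7 rule to each type of event that Section 7 can produce.

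**Inputs**
- Start of AE collection: signing of consent (Table 3, footnote l; Section 7).
- Window from consent to first dose: about 24 hours at most, assuming consent is signed at the start of screening (Table 3, footnotes a and h).
- Conditions present before consent: medical history (Section 7).
- TEAE rule: start at or after first dose, nothing more (Section 9.7).

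**Four cases**
1. *Onset after first dose.* The event is a TEAE, as it should be.
2. *Present before consent, worsens after first dose.* It is medical history until it worsens. The worsening then becomes the reportable AE, with a post-dose start, so it can count as a TEAE.
3. *Onset between consent and first dose, no worsening.* It is not a TEAE, as it should be.
4. *Onset between consent and first dose, worsens on study drug.* The AE already exists with a pre-dose start. If it keeps that start, it is not a TEAE.

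Cases 2 and 4 can describe the same clinical course on drug. They are classified differently only because the onset fell on one side or the other of the consent signature.

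**What case 4 loses.** It is absent from the system organ class and Preferred Term tables, from the severity and relationship breakdowns, and from the serious-TEAE output. It stays in the output of AEs leading to discontinuation, which 9.7 does not restrict to TEAEs. If it is serious, it also falls within the SAE summary that the synopsis describes, so 9.7 and the synopsis differ on that output.

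**Dependence on the recording rule.** There are two possibilities:
- Sites log the worsening as a new AE. Its start is then post-dose, 9.7 counts it, and the gap closes.
- Sites keep one record with the pre-dose start. The gap is then real. The fields that Section 7 lists include no date of severity change, so a worsening clause in 9.7 could not be applied from those fields alone.

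The protocol does not say which applies.

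**Effect of a wider definition.** Counting AEs that start, increase in severity or become serious at or after first dose brings in case 4 where it belongs and leaves cases 1 to 3 unchanged.

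**The case against.** The strongest reply is that nothing here is contradictory. Section 7 governs what is reported and Section 9.7 what is tabulated. The instruction "Any medical occurrences which are new or worsened from the time of informed consent and up to and including the final visit must be reported" can be read as making the worsening itself a fresh occurrence with its own post-dose onset. On that reading no event is lost. This stands as a condition on the point, but the protocol does not state that reading as a rule.

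A second reply is that the SAP, which is not shown, may define TEAEs more widely. That carries less weight. Section 9.7 explicitly leaves the criteria for potentially clinically significant values to the SAP, but it states the TEAE definition itself, so a wider definition in the SAP would depart from the protocol.

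Third, the exposure is narrow. The window is about a day at most, and study drug is to start as soon as possible after diagnosis. The four cardinal CABP symptoms are not AEs unless serious (Section 7.4). Laboratory, ECG and vital-sign changes are summarised from baseline and at their worst post-baseline value whatever the onset of an AE. All of this stands, and it is why the point is minor.

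Three stronger readings are tempting but unsupported:
- *A Day 1 AE without a start time cannot be classified.* Onset time is indeed collected only where available, but Section 9.8 assigns missing data for other safety outcomes to the SAP.
- *A particular number of the 550 subjects is affected.* No rate is given; zero is compatible with the text.
- *A change to 9.7 alone would need no new data.* The per-event fields in Section 7 include no date of severity change.

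**Conclusion.** The point holds as a minor one. The protocol states a start-only definition, and that definition misclassifies one identifiable type of event: an AE that begins between consent and first dose and worsens on study drug. The loss occurs only if such a worsening stays on the existing record, which the protocol neither requires nor rules out.

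Any effect is an under-count of TEAEs and of serious TEAEs. It is confined to events with onset in a window of about 24 hours at most, assuming consent is given at the start of screening. The number is probably small and cannot be derived from the protocol. A reader might infer that every safety output loses these events; that does not follow, because the discontinuation output in 9.7 and the SAE and death summaries in the synopsis carry no treatment-emergent limit. The difference between 9.7 and the synopsis on serious events should be resolved in any case.

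**What to change.** 1. In Section 9.7, define a TEAE as *an AE that starts, increases in severity or becomes serious at or after the first dose of study drug*.
2. In Section 7, state that when an AE with a pre-dose onset worsens after first dose, the worsening is recorded with its own date or as a new AE. Without this the wider definition cannot be applied reliably. Because 9.7 tabulates subjects with events, a second record under the same Preferred Term does not count a subject twice for that term.
3. Align the serious-event output in 9.7 with the synopsis: either summarise all SAEs in both places, with the treatment-emergent ones identified, or state the same limit in both.

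The cost is two small text changes (9.7 and its alignment with the synopsis) and one recording instruction for sites, with a matching entry in the eCRF completion rules if severity changes are not already dated there.
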